8.0 CRITERIA FOR DISCONTINUATION

8.1 Permanent Treatment Discontinuation

- 8.1.1 Treatment breaks longer than 3 weeks during combined chemotherapy and pelvic radiotherapy, or during brachytherapy.
- 8.1.2 Requirement for prohibited concomitant medications.
- 8.1.3 Completion of treatment as defined in the protocol.
- 8.1.4 Request by participant to terminate treatment.
- 8.1.5 Clinical reasons believed life threatening or no longer in the best interest of the participant by the site investigator, such as pregnancy or breastfeeding, even if not addressed in the toxicity section of the protocol.
- 8.1.6 Request by the investigator if s/he thinks the participant to be at significant risk of failing to comply with the provisions of the protocol as to cause harm to self

8.2 Premature Study Discontinuation

- 8.2.1 Request by the participant to withdraw.
- 8.2.2 Lost to follow-up. Lost to follow-up will be defined for this purposes of this study as 6 months of inability to contact or determine the participant's vital status, in spite of at least 3 documented attempts to contact the participant.
- 8.2.3 Request by the protocol chairs, AMC, IRB, NCI, OHRP, local government agencies, or pharmaceutical sponsors.

9.0 EVALUATION CRITERIA

9.1 Outcome Measures

The major parameters of the outcome measures are feasibility. Also, we will determine the safety and tolerability of concomitant chemoradiotherapy with cisplatin in HIV-infected women with LACC who are also receiving concomitant ART.

- 9.1.1 Treatment completion proportion is the proportion of subjects who enroll and complete the cisplatin/RT regimen.
- 9.1.2 Screening ratio is the number of potential participants screened per enrolled participant
- 9.1.3 Availability proportion is the follow-up completion proportion at 6 and at 12 months.
- 9.1.4 Safety and tolerability will be evaluated through tracking the number of dose delays, dose reductions, missing doses, and compliance

9.2 Exploratory Outcome Measures

- 9.2.1 Progression Free Survival is defined as the date from protocol registration to date of first documented reappearance (recurrence) or progression of disease or death. Since all subjects will be followed for 12 months after treatment, we will determine the 1-year PFS rate.
- 9.2.2 Recurrence is defined as increasing clinical, radiological or histological evidence of disease since study entry.
 - 9.2.2.1 Site of First Recurrence (e.g., para-aortic or supraclavicular lymph nodes, lung, liver, bone, etc.) will also be documented.
- 9.2.3 Overall Survival will be defined as observed length of life from entry to protocol to death; or for living participants, the date of last contact.
- 9.2.4 Local Control is coded as successful if no recurrence or disease progression is within the pelvic field. Persistence of tumor three months after completion of therapy will be coded as a failure. It is coded as a failure if there is any clinically documented evidence of recurrence or disease progression within the pelvic field.
- 9.2.5 Effects of treatment on the participant's HIV disease status will be determined by tracking the CD4 count, viral load, and concurrent AIDS-defining conditions.
- 9.2.6 Effects of treatment on the participant's HPV status, and the association of these factors with treatment outcomes, will be determined by measuring HPV DNA types and strain variants and gene methylation in cervical and anal swabs, and by measuring antibodies to HPV in serum.

10.0 DATA MANAGEMENT

CRFs will be provided for each subject via the AMC AdvantageEDCSM Internet Data Entry System upon enrollment. Data will be recorded on the CRFs using the unique subject identification number assigned at registration. Subjects must not be identified by name, initials, birth date, or any other personally identifying numbers or codes. Any study documents that are transmitted outside of the site must be labeled with the 9-digit subject ID number, protocol number, or other study-generated codes. Sample CRFs will be available on the AMC Operations and Data Management Center website.

10.1 Data Quality

It is the responsibility of the AMC Operations and Data Management Center to assure the quality of data for the study. This role extends from protocol development to generation of the final study database.

10.2 CRF Instructions

Instructions concerning the recording of study data on CRFs will be provided by the AMC.

10.3 Records to Be Kept

CRFs will be provided for each subject via the AMC AdvantageEDCSM Internet Data Entry System upon enrollment. Subjects must not be identified by name on any study documents. Data will be recorded on the CRFs using the unique subject identification number assigned at registration. Sample CRFs will be available on the AMC ODMC website (www.amcoperations.com).

10.4 Role of Data Management

Instructions concerning the recording of study data on CRFs will be provided by the AMC ODMC. The AMC Internet Data Entry System User's Guide can be found on the AMC ODMC web site (www.amcoperations.com). Each site is responsible for entering data and submitting forms according to the target submission dates set forth by the AdvantageEDCSM system.

It is the responsibility of the AMC ODMC to assure the quality of electronic data reported for each AMC study. This role extends from protocol development to generation of the final study databases.

11.0 STATISTICAL CONSIDERATIONS

11.1 Statistical Analysis Plan

Treatment completion rate will be estimated as proportion of all women who complete cisplatin of those who initiate cisplatin treatment. The binomial proportion and its 95% confidence interval will be used to estimate the treatment completion rate.

The screening ratio will be estimated as the number of patients screened divided by the number of patients enrolled on the study. The Poisson rate and its 95% confidence interval will be used to estimate the screening ratio.

The Kaplan-Meier method will be used to describe the progression-free survival (PFS) and overall survival (OS). We will generate KM curves for Stage I/II participants as well as Stage III/IV participants. The stratified log-rank test will be used to evaluate the association of HAART use, node positivity including enlarged pelvic nodes, stratified for stage. Those factors that are significantly associated with PFS and OS will be incorporated into a proportional hazards model. The one-year PFS and OS will be estimated using the cumulative proportion progression free (for PFS) or surviving (for OS) and its 95% confidence interval.

Frequency tables will be used to summarize the occurrences of adverse events by severity grade. Frequencies of specific adverse events will be tabulated.

Toxicity assessment: All toxicities will be reported on standard case report forms at visits and graded by NCI CTC v4.0. There will be standard dose reduction schedules. All dose delays, dose reductions, and missing doses will be tracked via CRFs during therapy. These will be tabulated and reported as rates.

Adherence assessments are planned weekly during cisplatin therapy and at the end of protocol therapy. Participants will be considered inadherent to ARV if they report missing doses on more than one adherence assessment. The proportion of participants who were inadherent to ARV during protocol therapy will be estimated using the binomial proportion and its exact 95% confidence interval.

To determine the HPV DNA types and HPV strain variants present in cervical cancer and in the anus of cervical cancer patients, frequency tables of HPV DNA types and HPV strain variants will be constructed for cervical and anal samples at baseline, end of treatment and at recurrence (if applicable). The binomial proportion and its 95% confidence interval will be used to estimate the proportion of each HPV DNA type and each HPV strain variant that occurs in at least 5% of patients in cervical or anal specimens. Concordance between anal and cervical specimens with respect to detection of specific HPV DNA types and HPV strain variants will be assessed using McNemar's chi-square test.

Changes in HPV DNA types and strain variants between baseline and post-treatment measurements will be assessed using McNemar's chi-square test for each DNA type and

strain variant. Proportional hazards models and logistic regression models will be used to evaluate the association of change in DNA types with progression free survival and local control, respectively.

The binomial proportion and its 95% confidence interval will be used to estimate the proportion of patients who have abnormally methylated genes for each gene tested.

Gene methylation profiles will be summarized at baseline.

Concordance between gene methylation profiles between cervical and anal swabs will be assessed at baseline using the kappa statistic.

The chi-square test will be used to assess the association between baseline gene methylation profiles and cervical persistence or recurrence.

The logistic regression model will be used to assess the effects of HPV-16 and HPV-18 serologic titer levels with disease persistence or recurrence using the logarithmic transformation for the titer levels. Similarly, the effects of changes in HPV-16 and HPV-18 titer levels from baseline to treatment on outcome measures (progression free survival, local control) will be assessed using proportional hazards models and logistic regression models.

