REGIMEN:	All participants with CD4 counts $> 200/\text{mm}^3$ ($0.2 \times 10^9/\text{L}$) will receive weekly cisplatin at a dose of $40 \text{ mg}/\text{m}^2$ concomitant with radiotherapy (external beam and brachytherapy). The first 3 participants with CD4 counts $\leq 200/\text{mm}^3$ ($0.2 \times 10^9/\text{L}$) will receive weekly cisplatin at a dose of $25 \text{ mg}/\text{m}^2$ with radiotherapy (external beam and brachytherapy). Based on review of the safety data from the first 3 participants, all other participants with CD4 counts $\leq 200/\text{mm}^3$ ($0.2 \times 10^9/\text{L}$) will receive weekly cisplatin at a dose of $40 \text{ mg}/\text{m}^2$ or no cisplatin with radiotherapy (external beam and brachytherapy). All participants will concomitantly receive combination antiretroviral therapy (ART) with an acceptable regimen that adheres to national guidelines for treatment of HIV infection.
PRIMARY OBJECTIVES:	
1) To determine if it is feasible to administer a regimen of cisplatin/RT in HIV-infected women with LACC on ART. This regimen is considered standard therapy for women with LACC who are not HIV infected. Feasibility will be assessed based on:
• Treatment completion proportion: the proportion of participants who complete the cisplatin/RT regimen• Screening ratio: the number of potential participants screened per enrolled participant• Availability proportion: follow-up completion proportion at 6 and 12 months2) To evaluate the safety and tolerability of concomitant chemoradiotherapy with cisplatin in HIV-infected women

EXPLORATORY AND FUTURE RESEARCH OBJECTIVES:

with LACC who are also receiving concomitant ART.

- 1) Determine the 1-year progression-free survival (PFS) of HIV-infected women with locally-advanced invasive cervical cancer (LACC) Stage IB, II, III, and IVA who receive weekly cisplatin concomitant with radiotherapy and ART.
 - Determine PFS in all registered participants, regardless of completion (intent to treat-ITT)
 - Determine the PFS in the subset of participants who complete the prescribed chemotherapy/radiotherapy
 - Compare PFS in these subjects with PFS of HIV-uninfected subjects as reported in the literature, stage for stage
- 2) To describe the effects of treatment on participants' CD4 counts, HIV viral load and concurrent AIDS-defining conditions

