2.2 Primary Objectives

- 2.2.1 To determine if it is feasible to administer a regimen of cisplatin/RT in HIV-infected women with LACC on ART. This regimen is considered standard therapy for women with LACC who are not HIV infected. Feasibility will be assessed based on:
 - 2.2.1.1 Treatment completion proportion – the proportion of participants who complete the cisplatin/RT regimen
 - 2.2.1.2 Screening ratio: the number of potential participants screened per enrolled participant
 - 2.2.1.3 Availability proportion: follow-up completion proportion at 6 and 12 months

2.2.2 To evaluate the safety and tolerability of concomitant chemoradiotherapy with cisplatin in HIV-infected women with LACC who are also receiving concomitant ART.

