4.2.2 Chemotherapy

Cisplatin 40 mg/m² IV over 30-60 minutes given weekly on days 1, 8, 15, 22, 29 and 36 for a total of 6 weekly cycles.

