4.6.1.2.4 Timing

HDR brachytherapy should start by week 4. When HDR brachytherapy begins, at least one implant will be performed per week with no external beam therapy given on the day of the insertion. If the majority of the external beam radiation has been given (>20 fractions), then two implants per week could be done separated by at least 72 hours in order to complete all treatment within eight weeks.

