6.2.6 Completion of Chemotherapy

If all 6 cycles of chemotherapy cannot be administered during external radiotherapy (whole pelvis and parametrial boost), the 6th cycle should be given during brachytherapy but not on the same day as brachytherapy.

Chemotherapy may not be given after completion of radiotherapy.

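### Section 11.1 estimates the primary endpoint from cisplatin completion among women who start cisplatin, whereas the synopsis, 2.2.1.1 and 9.1.1 define it as completing cisplatin and radiotherapy together

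*Combined protocol and SAP*

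**What the plan says.** Three places define treatment completion by both modalities. The synopsis has "Treatment completion proportion: the proportion of participants who complete the cisplatin/RT regimen". Section 2.2.1.1 uses the same definition, "the proportion of participants who complete the cisplatin/RT regimen". Section 9.1.1 brings in enrolment: "Treatment completion proportion is the proportion of subjects who enroll and complete the cisplatin/RT regimen".

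Section 11.1, which says how the rate will be computed, has "Treatment completion rate will be estimated as proportion of all women who complete cisplatin of those who initiate cisplatin treatment". It names cisplatin in both numerator and denominator and does not mention radiotherapy.

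Section 11.2 makes the treatment completion rate the primary outcome. It tests 0.50 against 0.70, treats 70% or above as sufficient for further study, and enrols 45 women to obtain 38 evaluable. The synopsis, 3.3 and 11.2 all use 'evaluable', and none defines it.

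On timing, 4.2.2 has cisplatin "given weekly on days 1, 8, 15, 22, 29 and 36 for a total of 6 weekly cycles". Section 4.6.8 plans for all radiotherapy to end on day 50 and no later than day 56. The modalities overlap: "HDR brachytherapy should start by week 4" (4.6.1.2.4), and if six cycles do not fit into external radiotherapy, "the 6th cycle should be given during brachytherapy but not on the same day as brachytherapy" (6.2.6). Section 6.2.6 also bars chemotherapy after radiotherapy is complete.

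**The concern.** The objective and the estimator describe different quantities. Finishing cisplatin does not show that radiotherapy was finished, because the planned cisplatin course ends two to three weeks before the planned end of radiotherapy. Under 6.1.3 and 8.1.1, a woman with a break of more than three weeks during brachytherapy is removed from protocol therapy. If she already had all six cycles, 11.1 still counts her as a completer.

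The denominators differ too. Section 11.1 drops enrolled women who never start cisplatin, while 9.1.1 leans towards counting them.

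The 70% criterion in 11.2 rests on this rate, and the introduction says the estimate will inform planning of a phase II trial. Two analysts, one following 9.1.1 and the other 11.1, could report different rates from the same data. Near 70% they could reach opposite conclusions, and the choice could be made after the results are known.

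**Working it through.** **The plan's own figures.** The dropout step reproduces: 38 / (1 − 0.15) = 44.7, rounded up to 45. The 38 does not reproduce at the printed one-sided level of 0.0510 with power 0.90. The normal approximation n = [(z(1−α)·√(0.5·0.5) + z(0.90)·√(0.7·0.3)) / 0.2]² gives 49.3, so 50. At one-sided 0.10 it gives 37.7, so 38. The printed level should be checked against the source document. That is a separate matter and nothing below depends on it.

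**Is 11.1 shorthand for the regimen?** Elsewhere, completion means both modalities: hypothesis 2.1.3 refers to completing the prescribed cisplatin and RT doses, and 2.3.1.2 to the prescribed chemotherapy and radiotherapy. Section 11.1 specifies cisplatin twice, so a literal analysis would ignore radiotherapy.

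**Direction.** Among N women who start cisplatin, let C complete it by the 11.1 criterion. Let F of those C fail to finish radiotherapy. Let S be women whose cisplatin is stopped under protocol rules (6.2.2, 6.2.5, 6.2.5.2) and who finish radiotherapy.

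- The 11.1 rate is C/N.
- If regimen completion requires the same cisplatin criterion, the regimen rate among starters is (C − F)/N, which cannot exceed C/N.
- If the S women count as completing the regimen as modified, the regimen rate is (C − F + S)/N, which exceeds C/N whenever S > F. The documents do not say how these women count, so in general the direction is open.

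**Size through the numerator.** Assume that all 45 enrolled women start cisplatin, that regimen completion requires cisplatin completion, and that true regimen completion is 0.60. Let q be the share of cisplatin completers who also finish radiotherapy; the documents give no value for q. The true 11.1 rate is then 0.60/q. Observing at least 70% of 45 needs 32 women (0.70 × 45 = 31.5). Exact binomial P(X ≥ 32 | n = 45):

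| q (assumed) | 11.1 rate, 0.60/q | P(at least 32 of 45) |
|---|---|---|
| 1.00 | 0.600 | 0.084 |
| 0.98 | 0.612 | 0.112 |
| 0.95 | 0.632 | 0.171 |
| 0.90 | 0.667 | 0.323 |

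**Denominator.** With 31 completers, counting one never-starter gives 31/45 = 68.9%, and leaving her out gives 31/44 = 70.5%. This shows what is possible, not how large the effect is likely to be.

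**What an all-enrolled denominator does to 11.2.** If 0.70 applies to all 45 enrolled, exact power is 0.836 for a cut-off of 29 or more (α 0.036) and 0.901 for 28 or more (α 0.068). If instead 0.70 applies to evaluable women and the planned 15% dropouts count as non-completers, the all-enrolled rate is 0.70 × 0.85 = 0.595. Exact power is then 0.30 (29 or more) or 0.42 (28 or more). The documents do not say which group 0.50 and 0.70 describe.

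**The case against.** The strongest reply concerns the denominator. Only 9.1.1 mentions enrolment; the synopsis and 2.2.1.1 say participants. Section 11.1 gives the only explicit denominator, and with 11.2 it can be read coherently, with evaluable women being those who start treatment. A treated-population denominator is defensible in a feasibility study if it is used consistently. Never-starters are also limited by design: enrolment falls within a week of treatment (3.5.2), radiotherapy must start within 7 days of enrolment (4.6), and 3.2.6 excludes women whose circumstances would prevent completion. This stands. All-enrolled is the better reading of 9.1.1, not an express requirement.

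On size, the values of q are assumed, and any proportion sitting at its threshold moves with one woman. This stands too: the figures illustrate sensitivity and do not predict bias. The schedule overlap also narrows the numerator gap, so disagreement would come mainly from unfinished brachytherapy.

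A reader might infer that 11.1 always overstates completion. The documents do not support that, because they do not say how protocol-directed cisplatin stops count. The synopsis also allows some later low-CD4 women "or no cisplatin with radiotherapy (external beam and brachytherapy", while 4.1.2 gives concurrent cisplatin to all participants and the run-in rules in 6.2.2 do not clearly assign later women to radiotherapy alone. Those passages must be reconciled separately.

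None of this answers the numerator conflict, which is explicit in three places.

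**Conclusion.** The mismatch is real and should be corrected before analysis. Followed literally, 11.1 reports cisplatin completion among initiators, which is not the stated primary outcome, and the 70% criterion would be judged on it.

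Among women who start cisplatin, the 11.1 rate can only equal or exceed the regimen rate, provided regimen completion requires cisplatin completion by the same criterion. Without that condition the direction is open. Under the stated assumptions (all 45 start, true regimen completion 0.60, q = 0.95), the chance of observing at least 70% about doubles, from 0.084 to 0.171. Over q from 0.98 to 0.90 it ranges from 0.112 to 0.323.

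A reader might also infer that a cut-off of 28 or 29 out of 45 could simply replace the present test with its power kept. That holds only if 0.70 describes all enrolled women, which the documents do not say.

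**What to change.** Numerator in 11.1: women who complete both the prescribed cisplatin and the prescribed radiotherapy (external beam plus brachytherapy). Fix one completion criterion before analysis, including how held, missed, reduced and protocol-stopped cycles count.

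Denominator: use one in the synopsis, 2.2.1.1, 9.1.1, 11.1 and 11.2. All enrolled is the better reading of 9.1.1. If a treated or evaluable group is kept for the 11.2 test, define it and also report the all-enrolled proportion.

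Keep cisplatin completion among initiators as a secondary estimate. State in 11.2 whether 0.50 and 0.70 refer to all enrolled or to evaluable women before adopting any cut-off for N = 45 or another N.

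Cost: no new data. Each participant's radiotherapy dose is already reviewed (4.6.6), and delays, reductions and missing doses are already on CRFs (11.1). The numerator change is wording. An all-enrolled denominator goes further, because the operating characteristics in 11.2 must be restated and the hypothesised rates or N may need revisiting. The reported completion rate may be lower.

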4.6.1 Standardized Radiotherapy

4.6.1.1 External Irradiation (IMRT will not be allowed on this study.)

All participants will receive 41.4-45 Gy external beam RT delivered to the pelvis in 23-25 fractions of 1.8 Gy. Treatments are to be delivered daily, five fractions per week and should be completed within 5 weeks \pm 3 days. Participants should be treated with bladder distention (although this is not mandatory), and bowel exclusion devices (e.g. belly boards) are allowed. If overall treatment time for external pelvic RT exceeds 38 days, the reason for the delay must be documented. If intracavitary RT cannot be performed, shrinking field technique should be performed to bring the gross tumor volume with adequate margins (minimum 1 cm) to a minimum total dose of 65 Gy. An attempt should be made to exclude all small bowel from treatment field after 50.4 Gy.

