4.6.1.1.1 Dose Specification

The dose to the pelvis shall be calculated at the intersection of the axes of the 4-field box. The dose to point B shall also be calculated using an off-axis calculation (or identified on the isodose distribution). In patients not undergoing brachytherapy, point B dose will be calculated at the point on pelvic side wall (at the level of superior wall of acetabulum). Heterogeneity corrected dose calculations are not allowed.

The dose to CENTRAL STRUCTURES shall be the sum of the dose at the intersection of the axes of the 4-field box and the dose to point A from the intracavitary treatment. The dose to SIDE WALL STRUCTURES shall be calculated bilaterally (reported separately) and shall be the sum of the dose at the intersection of the axes from the 4-field box plus the intracavitary dose to point B plus the contribution from the parametrial fields. For 2 dimensional planning, the dose at the central axis and pelvic side walls shall not differ by more than 10%. For 3 dimensional planning, the dose range shall be within 95% to 107% of the prescription dose.

Fractionation: Conventional fractionation will consist of one fraction per day, total five fractions per week.

Therapy interruptions: If interruption of radiation should occur for greater than two weeks, the protocol Radiation Oncology Study Chair must be notified.

Dose deviations: A discrepancy in dose (as specified in the protocol) of 6-10% and >10% will be considered as minor and major deviations from the protocol, respectively

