6.1.2.4 Dermatologic/Skin (Cutaneous) Adverse Effects

RT will not be delayed for moist desquamation, and if a break is felt to be clinically indicated, the Study Chair should be contacted prior to this break.

6.1.3 Participants with longer than a 3-week break during combined chemotherapy and pelvic radiotherapy, or during brachytherapy will be removed from the protocol-directed therapy. However, they should re-start radiotherapy off study as soon as the toxicities have improved to an acceptable level.

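### Section 11.1 scores the primary completion rate on cisplatin alone, although 2.2.1.1, the synopsis and 9.1.1 define it on the cisplatin/RT regimen, so a woman who finishes cisplatin and then stops radiotherapy counts as a success

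*Combined protocol and SAP*

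**What the plan says.** **Definition.** Objective 2.2.1.1 sets the treatment completion proportion as "the proportion of participants who complete the cisplatin/RT regimen", and the synopsis agrees. Section 9.1.1 repeats it: "Treatment completion proportion is the proportion of subjects who enroll and complete the cisplatin/RT regimen". The synopsis (Regimen) and 3.4 describe the radiotherapy as external beam and brachytherapy. Section 4.6 requires a target dose of 80-85 Gy to the primary disease, reached with the brachytherapy boost.

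**Estimation.** Section 11.1 is the only text that says how the rate is calculated: "Treatment completion rate will be estimated as proportion of all women who complete cisplatin of those who initiate cisplatin treatment". It gives a binomial proportion with a 95% confidence interval. Section 11.2 makes this rate the primary outcome, tests 0.50 against 0.70 in 38 evaluable patients, and treats 70% or above as enough to take the regimen forward. It does not redefine completion.

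**Timing.** Cisplatin is "given weekly on days 1, 8, 15, 22, 29 and 36 for a total of 6 weekly cycles" (4.2.2). The general schedule in 4.6.8 starts brachytherapy after day 35 and ends all RT at day 50, day 56 at the latest. For HDR, 4.6.1.2.4 asks for a start by week 4.

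**Removal and fallback.** Section 6.1.3: "Participants with longer than a 3-week break during combined chemotherapy and pelvic radiotherapy, or during brachytherapy will be removed from the protocol-directed therapy". Section 8.1.1 lists the same breaks as grounds for permanent treatment discontinuation. Section 4.6.1.1 provides an alternative: "If intracavitary RT cannot be performed, shrinking field technique should be performed to bring the gross tumor volume", to at least 65 Gy. Section 4.6.1.1.1 also foresees such women: "In patients not undergoing brachytherapy, point B dose will be calculated at the point on pelvic side wall".

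**The concern.** The objective and the outcome definition need two components; the estimator needs one. The second component usually finishes two to three weeks after the first, so a woman can satisfy 11.1 before her RT is complete, and nothing that happens to her RT afterwards changes her score.

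Whether a full course including brachytherapy can be delivered at these sites is part of the feasibility question. If 11.1 is applied literally, the regimen could be taken forward partly on women who did not complete it. Two analysts, one following 9.1.1 and one following 11.1, could also report different primary results from the same data.

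**Working it through.** **1. The two rules applied to the same woman**

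| Course | Under 11.1 | Under 9.1.1 |
|---|---|---|
| Finishes cisplatin, external beam and brachytherapy | Success | Success |
| Stops cisplatin early, whatever happens to RT | Failure | Failure |
| Finishes cisplatin, then removed for a brachytherapy break of more than 3 weeks (6.1.3, 8.1.1) | Success | Failure |
| Finishes cisplatin, treated on the 4.6.1.1 external-beam fallback | Success | Not stated |
| Enrolls but never starts cisplatin | Not in denominator | In denominator, failure |

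The third row is a direct contradiction. The fourth is settled by 11.1 but not by 9.1.1: the woman did not receive brachytherapy, yet she completed the RT that the protocol directs for her. The fifth is a separate difference in denominator within the same 11.1 sentence.

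**2. Where the rules can diverge.** Section 6.2.3 bars cisplatin during an RT delay, and 6.2.6 bars it after RT ends. A woman whose external beam is interrupted or cut short therefore tends to lose cisplatin cycles and to fail 11.1 as well. What 11.1 misses is mainly brachytherapy lost around or after the last cisplatin dose.

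**3. The plan's own figure.** Inputs from 11.2: p0 = 0.50, p1 = 0.70, power 0.90, one-sided level printed as 0.0510.

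n = [(z(1-α)·√(p0·q0) + z(power)·√(p1·q1)) / (p1 - p0)]²

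- α = 0.051: [(1.635 × 0.5 + 1.282 × 0.458) / 0.20]² = 49.3, so 50. This does not give 38.
- α = 0.10: [(1.282 × 0.5 + 1.282 × 0.458) / 0.20]² = 37.7, so 38. This matches.
- Dropout: 38 / 0.85 = 44.7, so 45. This matches.

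The printed level is a separate point. It matters here only because the pass mark is uncertain. At n = 38 the exact null tails are P(X ≥ 24) = 0.072, P(X ≥ 25) = 0.036 and P(X ≥ 27) = 0.007. A cutoff of 25 fits a level of 0.05 and 24 fits 0.10. If the observed rate itself must reach 70%, the cutoff is 27 (27/38 = 71%).

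**4. Illustration of size.** Let q be the share of cisplatin completers who do not complete RT. The documents give no value; 5, 10 and 15% are assumptions. Regimen completion is c(1 - q), where c is cisplatin completion. With true regimen completion at the null of 0.50, c = 0.50/(1 - q), and the chance of passing under 11.1 is P(X ≥ r) for a binomial with n = 38 and rate c.

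| q | c | r = 24 | r = 25 | r = 27 |
|---|---|---|---|---|
| 0 | 0.500 | 0.072 | 0.036 | 0.007 |
| 5% | 0.526 | 0.127 | 0.071 | 0.016 |
| 10% | 0.556 | 0.219 | 0.134 | 0.037 |
| 15% | 0.588 | 0.356 | 0.241 | 0.084 |

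In counts: if one of 25 counted completers did not finish RT, 25/38 (one-sided p = 0.036) becomes 24/38 (p = 0.072); if two, 23/38 (p = 0.128).

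**5. Power if 0.70 was meant for cisplatin alone.** Regimen completion is then 0.70(1 - q) = 0.665, 0.630, 0.595. Exact power falls from 0.863 to 0.732, 0.564, 0.388 (r = 24), or from 0.774 to 0.611, 0.431, 0.269 (r = 25).

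**The case against.** The strongest reply is that 11.1 is shorthand and the practical gap is small. Cisplatin completion already captures part of RT failure, for the reason in step 2 of the working. Where HDR starts by week 4 it overlaps cisplatin, and 6.2.6 places a late sixth cycle during brachytherapy. Sites must have capacity for the full treatment (3.4), and women whose circumstances will not permit completion are excluded (3.2.6). RT shortfalls would not be hidden either: each RT record is reviewed centrally (4.6.6) and brachytherapy compliance forms are submitted (Appendix XII).

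Most of this stands as a limit on size. It does not repair the rule. Section 11 has no RT completion proportion to fill the gap, and hypothesis 2.1.3 shows that the protocol elsewhere asks for both the cisplatin and the RT doses.

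A reader might infer more than the documents support in three ways:

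- That every woman who misses or stops brachytherapy is a success. She is one under 11.1 only if she also finished cisplatin.
- That a woman on the 4.6.1.1 fallback must be a failure, or that her score is nowhere given. Section 11.1 counts her if she finishes cisplatin; only her status under 9.1.1 is open. Calling a protocol-directed alternative a failure is a choice, not something the text dictates.
- That the false-pass risk is known to be large. The higher figures need both an assumed 15% and a lower pass mark.

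**Conclusion.** The concern holds as a wrong scoring rule for the primary outcome: 11.1 omits the RT condition that 2.2.1.1, the synopsis and 9.1.1 impose. The woman who finishes cisplatin and is then removed during brachytherapy shows that the two rules give opposite answers. The denominators conflict as well.

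The size cannot be determined from the documents and may be low. The pass probabilities in the working are illustrations under assumed rates, with true regimen completion set at the null and 38 women scored. They show that the decision is sensitive to one or two women, not that the trial's error rate is in fact inflated by those amounts. The documents also do not show whether the 0.50 and 0.70 benchmarks were meant for cisplatin alone or for the whole regimen, which is a reason to settle the definition before analysis.

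**What to change.** In 11.1, count a woman as a completer only if she completes cisplatin and the protocol RT (external beam plus brachytherapy), in line with 9.1.1. Use one denominator in 9.1.1 and 11.1: either all who enroll or all who start cisplatin. State that women removed under 6.1.3 or 8.1.1 after finishing cisplatin stay in that denominator as non-completers.

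Report how many women were treated on the 4.6.1.1 no-intracavitary fallback. Give the rate with and without them as completers, and have the sponsor name in advance which is primary. Report cisplatin-only completion as a secondary figure, so that the quantity 11.1 now describes is still available.

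The cost is a few sentences. The RT records and brachytherapy forms are already collected, and the planned 38 evaluable and 45 enrolled need not change. The downside is a lower reported rate. If the 70% target was set for cisplatin alone, power also falls as in step 5; the sponsor should then say so and reconsider the benchmark. If cisplatin alone was truly intended, 2.2.1.1, the synopsis and 9.1.1 need to be changed instead.
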